## Synopsis

Titel	"An exploratory study regarding the use of the biomarker DAT for image diagnosis of clear cell renal cell carcinoma"
Developmental Phase	Phase 2
Background	
The background to why the study should be done
 
Kidney cancer affects approximately 1000 people a year in Sweden and globally, approximately 340,000 people are diagnosed with this disease. The most common form of kidney cancer is clear cell renal cell carcinoma (ccRCC), which accounts for about 80% of all cases. Despite some treatment progress, over 40% of patients who suffer from kidney cancer die. The presence of this tumor form is increasing globally and the annual growth rate is estimated at 6.25% in the period 2013-2023. Localized kidney cancer has good prognosis; The tumor, or tumor-bearing kidney is usually surgically removed. However, the symptoms of renal cancer are diffuse and in about 25% of cases, the disease has already spread beyond the kidney at the time of diagnosis. An additional 25% of patients with localized disease later display metastases, although the first analysis showed that the disease was limited to the kidney. For patients with metastatic disease, the prognosis is very poor, as kidney cancer does not respond to common cancer treatments such as cytostatics and radiation and less than 10% of these patients are expected to survive for five years. It is therefore crucial to be able to clarify the spread of the disease. Today there are no diagnostic methods that can specifically detect kidney cancer and distinguish between subtype of renal cancer. Small metastases are likely

	
to be missed by today's methods. The need for new diagnostic methods is therefore eminent.
 
We have identified the molecule Dopamine Transporter (DAT) as a new, highly specific, biomarker for clear cell kidney cancer. This molecule is usually only expressed in the brain of dopaminergic neurons, but we have now shown that it is found to be very high in clear cell kidney cancer, but not in other cancers. DAT is used today in the diagnosis of Parkinson's disease. DaTSCAN is a radioactively labeled substance that binds to DAT and thus to dopaminergic neurons. The signal from the binding can be detected using SPECT camera and a decreased signal is evidence of loss of dopaminergic neurons and thus Parkinson's disease, which then can be distinguished from other neurodegenerative diseases. This study aims at investigating whether clear cell kidney cancer can be detected by a DaTSCAN analysis, where in this case an increased signal is expected, unlike Parkinson's diagnostics

Study design
	
Open single arm trial with a small number of patients (10) for proof of concept of the use of DaTSCAN for the detection of clear cell RCC. Recruited patients with suspected dissiminated kidney cancer will, after informed consent to participate in the study, be investigated using CT and DaTSCAN followed by SPECT. DaTSCAN is injected intravenously and followed by SPECT examination 5h later. The images from the DaTSCAN investigation will be analyzed and anatomically compared to CT examination of the patient. Any side effects of the study will be reported.


Objectives
	
The main objective is to investigate whether DaTSCAN with subsequent SPECT can detect elevated DAT levels in at least one lesion identified with CT in patients with clear cell renal cell carcinoma, as assessed by pathologist?
 
DaTSCAN signal will be seen as positive, when displaying intensity <math>\geq 3</math>ggr higher than the background and correlating anatomically with at least one lesion found with CT.
 
DaTSCAN is used routinely to detect the loss of dopaminergic neurons in the striatum of patients with clinically uncertain Parkinsonian Syndromes. The active substance in DaTSCAN, Ioflupane specifically binds to DAT. By analyzing the focal uptake of Ioflupane (123I) with SPECT / CT the progression of the disease may be clarified. In light of our findings that clear cell renal cancer express significantly elevated levels of DAT, we postulate that DaTSCAN can be used for detection of clear cell renal cell carcinoma.
 
The exploratory objective is to investigate whether:

	
 
• DaTSCAN with subsequent SPECT, by detecting elevated levels of DAT in clear cell renal cancer, can be used to distinguish clear cell renal cancer from other subtypes of renal cancer such as papillary renal cell cancer, chromofob kidney cancer and benign tumors such as oncocytoma?
 
• Surgically removed DaTSCAN positive lymph nodes exhibit infiltration of clear cell renal cell carcinoma cells, regardless of the CT status?
 
• DAT-mRNA expression in primary tumor correlate with DaTSCAN signal where the surgically removed tumor material with high DaTSCAN intensity also exhibit high mRNA levels of DAT?
 


Study population
 
Inclusion and exclusion criteria
	
This study is an exploratory single-arm study at Skåne University Hospital. The study intends to include 10 patients, if one of the research subjects withdraws from the study, this subject will be replaced so that the number of persons is 10 in total. After 10 analyzed patients, an evaluation is made. If less than 8 patients out of the 10 analyzed have been diagnosed as ccRCC by pathologist, an additional 3 patients will be included. Each patient will be evaluated continuously after completion of the study. For ethical reasons, the study will be terminated if 4 patients diagnosed with clear cell kidney cancer by pathologist, all display negative DaTSCAN signal in primary tumor.
 
The patients / research subjects will be recruited through the Urological Clinic in Malmö.
 
The DaTSCAN study will be conducted at the department of Clinical Physiology / Nuclear Medicine VO Image and Function in Malmö
 
Pathologic assessment of surgically removed material from each study subject will be obtained from the Pathological Clinic in Malmö
 
This study plans to include subjects that comply to the following inclusion and exclusion criteria:
 
Inclusion criteria
 
 
-suspected kidney cancer diagnosis
 
-suspected spread of the cancer
 
-the patient is scheduled for surgery alternatively biopsy of kidney tumor
 
-the patient is 18 years or older
 
-the patient has given their consent to participate in the study
 
 
Exclusion criteria
 
 
-known or suspected allergy to the active substance in DaTSCAN,
 

	
ioflupane or any of the following ingredients:
 
 
• Sodium acetate
 
• Acetic acid
 
• Ethanol
 
 
-the patient suffers from moderate to severe liver disease with liver enzymes (transaminases)> 2 times the upper limit
 
-the patient suffers from moderate to severe renal impairment and exhibits GFR <40
 
-the patient is medicated for Parkinson's disease
 
-the patient is medicated with any of the following medications:
 
 
• Amphetamine
 
• benztropine
 
• Bupropion
 
• Cocaine
 
• mazindol
 
• Methylphenidate
 
• Phentermine
 
• Sertraline
 
• levodopa (Sinemet, Pharma Copa, Atamet, Stalevo, Madopar, Prolopa)
 
 
-the patient is /or plans to become pregnant
 
-breastfeeding
 
-the patient suffers from mental inability, unwillingness or language difficulties resulting difficulty in understanding the meaning of taking part in the study

Methodology
	
Patients with suspected renal cancer are screened for the suitability to participate in the study.
 
After informed consent, a 3-phase CT examination of abdominal and thoracic baseline for tumor burden is performed. If an equivalent CT scan was performed in Region Skåne <28 days before the inclusion date, this study will be the basis of the baseline for tumor burden.
 
Thereafter, the patient is scheduled for DaTSCAN examination, which is performed before any surgery. Prior to DaTSCAN injection the patient takes potassium iodide tablets, according to local clinical practice for DaTSCAN studies, to protect the thyroid gland. At the time of investigation of DaTSCAN, the patient is slow-paced injected with the DaTSCAN solution in the arm, not faster than 15 seconds. The patient then waits for 5h before image diagnosis with abdomen / thoracic SPECT / CT is performed.
 
Possible side effects are documented.
 
The collected image material is analyzed and compared for anatomical localization with previously performed CT examination.

	
Two days after the DaTSCAN study, the patient is contacted for follow-up of possible side effects following the study. Pathological assessment statement collected from pathologist after surgery / biopsy.
 
If the patient has consented to biobanking tissue samples from removed tumor according to ethical approval: LU680-08 and LU289-07, mRNA levels of DAT are also analyzed for these samples.
 
The study closes after 10 patients are subjected to DaTSCAN-examination, the results have been analyzed and pathological responses are obtained. The study is expected to end after 1 year.
 
For ethical reasons, an early stopping rule is applied if four patients with pathologically verified ccRCC display negative signal from the DaTSCAN examination, the study is in that case ended.

Test product	
Test product, dose and mode of administration, batch number:
 
Test product  Substance Generic Name: Ioflupan (I-123), Product Name: DaTSCAN, ATC Code: V09AB03  Pharmaceutical form and strength: Solution for injection 74MBq/ml, Manufacturer: GE Healthcare  DaTSCAN was ordered from GE Healthcare, and provided with patient-specific labeling by the clinician responsible for administering DaTSCAN to patient.
 
Mode of administration:  The patient takes potassium tablets prior to the examination, to protect the thyroid gland. At the time of the DaTSCAN examination, the patient is injected intravenously at slow rate with 185MBq DaTSCAN solution. Using a dose calibrator, 185MBq of DaTSCAN is drawn into the syringe to be given to the research person. A label is printed and put on the syringe with the following information: patient name, drug, batch, dose and draw time. Thereafter, the drug is administered directly to the patient. Afterwards, the remaining activity in the syringe is measured and the exact dose is recorded in the patient's journal. The patient then waits for 5h before performing diagnostic examination with SPECT.

Evaluations	
Criteria for evaluation:  Each patient is continuously evaluated after completion of the DaTSCAN-examination and analysis.
 
Efficacy  Analysis of the image material from the SPECT study  Signal from DaTSCAN is quantified and compared with an internal control in the form of the previous CT imaging. DaTSCAN signal is considered positive when <math>\geq 3</math> times higher than background and correlating anatomically with at least one lesion found with CT.
 
Pathological assessment

	
The patient's surgically removed tumor/metastasis will be examined by a pathologist for kidney cancer subtype determination. This assessment will be compared to the DaTSCAN expression. If patients with pathologically verified ccRCC tumor also have positive DaTSCAN signal, the DaTSCAN study will be considered to detect clear cell kidney cancer.
 
mRNA levels of DAT in tumor tissue from biobank
 
In the cases where the recruited research persons have given consent to that material from surgery/biopsy is save for research (biobank) in accordance with licence number LU680-08 and LU289-07, these samples will be requested from the biobank. These samples will be examined for mRNA levels of DAT and then compared to DaTSCAN signal in the same tissue to investigate any correlation.
 
Safety
 
Potential Adverse Events is registered at each study visit.
 
 
• When injecting DaTSCAN (Ioflupan I123)
 
• Immediately after the SPECT investigation
 
• 2 days after the DaTSCAN survey (through telephone interview from research nurse)
 
 
The incidents may be observed by a doctor / nurse or reported by the subjects themselves. At each study visit (above), an open question is asked to the subjects: "Have you had any health problems since taking potassium iodide?"

End of Study	
The patient / research subject can end their participation in the study at any time without any consequences for his/hers further treatment.
 
The doctor / sponsor may suspend the patient's participation in the study at any time e.g. because of adverse effect or that the subjects does not comply the study protocol.
 
If the research subject exhibits hypersensitivity reaction of the DaTSCAN injection, the patient does not need to proceed to SPECT examination.

Statistical plan	
As this is an exploratory study with a low number of patients, thus there is no basis for a power calculation. However, assuming that the proportion of clear cell kidney cancer (ccRCC) is 80% of all kidney cancer cases, we plan to include 10 patients with the probability that at least 6 patients had ccRCC of 96,7% and with a probability of 8 ccRCC patients of 67,8%. The results will be presented with descriptive statistics. An exploratory objective is whether DaTSCAN can be used for differential diagnosis of renal cancer. With a recruitment of 10 renal cancer patients, there is 62.4% probability that we include 2 patients of non-clear cell subtype.

Adverse Events
	
Incidents will be registered at each study visit. That is on the following occasions:
 
When injecting DaTSCAN (Ioflupan I123)  Immediately after the SPECT investigation  2 days after the DaTSCAN investigation
 
On these occasions, open questions will be asked to the subjects: "Have you had any health problems since taking potassium iodide?"
 
The incidents may be observed by a doctor / nurse or reported by the subjects themselves. Incidents are entered into patient records and subsequently recorded in CRF. Assessment of relationship, severity and seriousness is done by the investigator in CRF. As a minimum, registered for each incident: description of the incident, start and stop, relationship, severity, and if considered serious, actions and outcomes. All serious side effects will be followed until they are restored or until confirmed by the examiner as no longer necessary to follow these incidents.

Potential benefit:
	
In a longer perspective, a new method of renal cancer imaging would be of great importance Today, many cases of small metastases that require systemic treatment missed. Through a more accurate picture of the spread of the disease, treatment could be adapted.

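### The lymph-node objective examines only DaTSCAN-positive removed nodes, so it cannot separate an association from the base rate or count removed infiltrated nodes that the scan missed

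*Combined protocol and SAP*

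**What the plan says.** The Synopsis (Objectives) lists three exploratory questions. The second is whether "Surgically removed DaTSCAN positive lymph nodes exhibit infiltration of clear cell renal cell carcinoma cells, regardless of the CT status". The unit studied is a removed node with a positive signal, and the outcome is infiltration by ccRCC cells.

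Other parts of the Synopsis bear on it:

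- **Inclusion criteria:** patients must have "suspected spread of the cancer". Tissue comes from patients for whom "the patient is scheduled for surgery alternatively biopsy of kidney tumor" holds, so node removal is not required and biopsy-only patients are eligible.
- **Study population:** "Pathologic assessment of surgically removed material from each study subject will be obtained from the Pathological Clinic in Malmö". This is not restricted by scan result.
- **Evaluations, pathological assessment:** tumor or metastasis is examined for subtype, and "This assessment will be compared to the DaTSCAN expression". Nodes and infiltration are not mentioned.
- **Objectives and Evaluations, positive signal:** the signal must be at least 3 "times higher than background and correlating anatomically with at least one lesion found with CT".
- **Statistical plan:** results are descriptive, and no analysis or number is given for nodes.

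**The concern.** Restricting the question to positive nodes fixes one margin of the two-by-two table and discards the other row. What remains is the positive predictive value (PPV) among removed nodes. A PPV has meaning only against the base rate, here the infiltrated share of all removed nodes, and the plan does not ask for that share or for the share among negative nodes. An informative scan and an uninformative one can therefore return the same result.

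The restriction also drops removed nodes that are infiltrated but show no signal. The Background says that small metastases are probably missed by present methods, and Potential benefit looks ahead to a more accurate picture of spread. Missed disease is a question of sensitivity, which positive nodes alone cannot address. In a very small series, a striking result such as 5/5 is easily over-read when nothing stands beside it.

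**Working it through.** **The plan's own figures.** None is stated for nodes. The recruitment probabilities are binomial tails with n = 10: P(at least 6 ccRCC; p = 0.8) = 0.967, P(at least 8 ccRCC; p = 0.8) = 0.678 and P(at least 2 non-clear cell; p = 0.2) = 0.624. They reproduce the stated 96.7%, 67.8% and 62.4%, the last two when read as 'at least'. They describe subtype mix and do not bear on nodes.

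**Inputs.** The documents give neither the base rate of infiltration among removed nodes (π) nor any node count. All values of π, sensitivity (Se), specificity (Sp) and node numbers below are assumptions, and nodes are treated as independent.

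**Step 1: what positives alone estimate.**

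PPV = Se·π / [Se·π + (1 − Sp)(1 − π)].

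If signal and infiltration are unrelated, Se = 1 − Sp and PPV = π.

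**Step 2: range over π.** The accurate scan has Se = Sp = 0.9. At π = 0.3, for example, PPV = 0.27 / (0.27 + 0.07) = 0.79. The last column is π⁵.

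| π | PPV, uninformative scan | PPV, accurate scan | Chance of 5/5 infiltrated, uninformative scan |
|---|---|---|---|
| 0.3 | 0.30 | 0.79 | 0.2% |
| 0.5 | 0.50 | 0.90 | 3.1% |
| 0.7 | 0.70 | 0.95 | 16.8% |
| 0.9 | 0.90 | 0.99 | 59.0% |

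At a low base rate, 5/5 would be informative. At a high one it would not. The reader of the result will not know which applies.

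**Step 3: what negative nodes add.** Suppose 5 of 5 positive nodes are infiltrated. The exact 95% interval has lower limit 0.025^(1/5) = 0.48, so it runs from 48% to 100%, whatever the negative nodes show.

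- Negative nodes 0/5 infiltrated: Fisher's exact two-sided p = 2/252 = 0.008.
- Negative nodes 5/5 infiltrated: p = 1.0.

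The p-values only show how far apart the two situations are. No test is proposed.

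**Step 4: missed nodes.** Suppose 10 removed nodes are infiltrated, the scan flags 2 of them, and it flags no uninvolved node. The objective reports 2/2 = 100%. Sensitivity among removed nodes is 2/10 = 20%.

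**Step 5: CT status.** The objective applies whatever CT showed, but the positivity definition needs an anatomical match to a CT lesion. Applied node by node, a node with high uptake and no CT lesion cannot be called positive, so the CT-negative part of the objective would be empty by definition.

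**The case against.** The strongest reply is that the objective does what it says. It asks whether positive nodes are infiltrated and does not claim that the signal predicts infiltration or that sensitivity will be measured. DAT is described as normally confined to the brain, so whether nodal uptake means ccRCC is a natural question for an "Open single arm trial with a small number of patients (10) for proof of concept" reported descriptively. The benefit of finding small metastases is placed in a longer perspective. This stands in part: the share among positives is legitimate and should stay. The comparison asked for is equally descriptive and needs no extra patients or power calculation.

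It can also be said that pathology is compared with DaTSCAN in any case, without restriction to positive signals. That is true for subtype of tumor or metastasis, but it is not a plan for node-level infiltration.

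Four stronger readings are tempting, and the documents do not support them:

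- *The negative-node data are sure to exist.* Node removal is not required, biopsy-only patients are eligible, and node-by-node pathology reporting is not promised. There may be few nodes or none.
- *Suspected spread means a high base rate among removed nodes.* It is a patient-level criterion and names no site. A high rate is possible but not established.
- *The positives-only figure is worthless.* At a base rate of 30%, 5/5 would be unlikely by chance (0.2%).
- *The fuller table would give the scan's sensitivity for nodal disease.* Only removed nodes have pathology, so infiltrated nodes left in place remain uncounted.

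**Conclusion.** The concern holds as a limit on what one exploratory objective can show. As worded, it yields only the infiltrated share of positive removed nodes. It cannot distinguish an association from the base rate, and it leaves out removed infiltrated nodes that the scan missed.

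The logic needs no assumption. Its practical size depends on a base rate and a node count that the documents do not give. With the base rate assumed between 0.3 and 0.9, an uninformative scan would give an expected share of 30% to 90% and would produce 5/5 with probability 0.2% to 59.0%. Clustering of nodes within patients would make such results less secure than these figures suggest.

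The conflict between the positivity definition and the objective's disregard of CT status is a separate textual point that must be settled before any node table can be filled in. The main objective, the stopping rule and safety are not affected by the missing node comparison. This is a worthwhile, inexpensive improvement.

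**What to change.** 1. Extend the objective to all surgically removed nodes, or node stations, in patients with pathologically verified ccRCC. List nodes from patients with other diagnoses separately, since the outcome is infiltration by ccRCC cells.
2. Prespecify a cross-tabulation of DaTSCAN positive/negative against infiltrated/not infiltrated, split by CT status. Report the infiltrated share among positive and among negative nodes, and the share of infiltrated nodes that were positive. Give node and patient counts throughout, because nodes cluster within patients.
3. State that the last of these shares applies to removed nodes only, and that few or no nodes may be available.
4. For this table, classify nodes by the signal ratio alone. Reconcile the positivity definition in Objectives and Evaluations with the objective's wording on CT status.

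**Cost.** One reworded objective and one descriptive table, with no extra patients. Removed nodes must be matched to the image; positive nodes already need this, but extending it to negative ones may require clearer surgical labelling and pathology reporting. Reported performance may look less favourable than a positives-only figure.
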